16.1.5. SENSITIVITY ANALYSES FOR PRIMARY EFFICACY ENDPOINT

As a sensitivity analysis to the handling of missing data in the analysis of the primary efficacy endpoint, the primary analysis of the primary efficacy endpoint (Section 16.1.4) will be repeated with multiple imputation for intercurrent events. For participants who are in FPAS but (1) do not have a SARS-CoV-2 RT-PCR-positive symptomatic illness status occurring post dose of IMP and withdraw from the study prior to the time of analysis, or (2) were unblinded to treatment assignment prior to having met the criteria for the primary efficacy endpoint, or (3) received COVID-19 vaccine or other preventive product prior to having met the criteria for the primary efficacy endpoint, their event status will be imputed assuming the observed event rate per treatment group conditional on stratification factors using multiple imputation techniques as described in the following paragraphs.

The primary analysis using Poisson regression with robust variance requires a participant-level dataset. A repeated imputation approach is introduced to impute the status of SARS-CoV-2 RT-PCR-positive symptomatic illness occurring post dose of IMP for missing observations at the participant level for the model fitting. By incorporating the between-imputation variance, a reliable statistical inference in both hypothesis testing and CI estimation of the treatment effect is expected through the repeated imputation (Little and Rubin, 2002). In the primary analysis the missing outcome for participants who drop out (e.g., withdrawal, lost to follow-up, death not caused by SARS-CoV-2, etc.) prior to reaching cut-off time for analysis without a SARS-CoV-2 RT-PCR-positive symptomatic illness occurring post dose of IMP will be imputed per stratum determined by the stratification factor using observed event rate per treatment group. The imputation and subsequent analysis may be carried out using SAS PROC MI (Monotone Logistic Regression Method) and SAS PROC MIANALYZE. The detailed imputation steps are described as follows.

- Step 1: Missing events in both arms will be imputed with the observed event rate per treatment group. The imputation may be executed using SAS PROC MI (logistic regression method with the recoded treatment term and stratification factor), or random sampling from an appropriate distribution. The random seed is 10021.
- Step 2: A complete dataset comprises the imputed SARS-CoV-2 RT-PCR-positive symptomatic illness status and observed SARS-CoV-2 RT-PCR-positive symptomatic illness status.
- Step 3: Analyze the complete dataset using a Poisson regression model with robust variance to estimate the RR on the incidence of SARS-CoV-2 RT-PCR-positive symptomatic illness between AZD7442 and placebo, with the term of treatment group and the stratification factor. The point estimate of log-transformed RR and its variance will be extracted from the model.
- Steps 1-3 will be repeated 20 times. SAS procedure PROC MIANALYZE will be used to combine inferences from the 20 completed datasets, that will result in a combined point estimate of log-transformed RR and the

variance.

A sensitivity analysis of the primary endpoint, in which participants who were seropositive by any test for SARS-CoV-2 pre-dose of IMP are excluded, may be performed.

16.1.6. SUPPLEMENTARY ANALYSES FOR PRIMARY EFFICACY ENDPOINT

As a supplementary analysis, the primary analysis of the primary efficacy endpoint (refer to Section 16.1.4) will be repeated including region (Section 7.7) as an additional covariate to assess the robustness of the efficacy results, if data permit.

To support the primary analysis, time to event (i.e., the duration in days from dose to first event or censoring) analyses will be performed as follows. A Cox proportional hazard (PH) model, stratified by age group at informed consent (Section 7.6) with treatment group as the only covariate, will be fitted to the data, and the Efron method will be used to control for ties. The hazard ratio and corresponding 95% CI from the Cox PH model will be presented. Kaplan-Meier curves with log-rank test p-value will also be presented by treatment arm.. Corresponding descriptive statistics for the active and control groups will also be produced.

In addition, the absolute risk reduction of AZD7442 over placebo in preventing the incidence of the SARS-CoV-2 RT-PCR positive symptomatic illness prior to Day 183 will be presented, along with the 2-sided 95% CI using the Miettinen and Nurminen's score method (Miettinen and Nurminen, 1985). The absolute risk reduction (ARR) will be implemented using the SAS PROC FREQ procedure.

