4.4. PRIMARY ANALYSIS

The primary analysis will occur after approximately 24 primary endpoint events have been confirmed across the active and control groups or 30% of study participants have become unblinded (at which point the ability to observe primary endpoint events is expected to have diminished), whichever occurs earlier. All primary endpoint events accrued up until the data cut-off (DCO) will be included in the primary analysis. The date for the DCO for this analysis will be the date that the 24th primary endpoint event is confirmed or the date that 30% of study participants have become unblinded, whichever occurs earlier.

All planned primary analyses are detailed in this SAP and will be performed by AstraZeneca or its delegates following Sponsor authorization of this SAP, Sponsor authorization of the analysis sets, database lock (DBL), and

analysis team unblinding. The primary analysis will be carried out by an unblinded analysis team, and the procedure will be detailed in an unblinding plan; participant level unblinding information will be kept strictly confidential, and rationale for any unblinding will be documented.

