7.1. SAMPLE SIZE CALCULATION

Approximately 5150 participants will be randomized in a 2:1 ratio to receive a single IM dose of AZD7442 (divided in 2 sequential injections, one for each mAb component) (the active group, n = approximately 3433) or saline placebo (the control group, n = approximately 1717) on Day 1.

The sample size calculations are based on the primary efficacy endpoint and were derived following a modified Poisson regression approach (Zou 2004). All participants will be followed for the entire duration of the study.

With at least 18 observed events, assuming 80% true efficacy, the study will have approximately 90% power to demonstrate that the lower bound of the 2-sided 95% CI for efficacy is greater than 0 (see Table L:).

Table L: Simulated Power by Number of Observed Events

$\lambda_{Placebo}$	$\lambda_{AZD7442}$	Observed Events	Simulated Power
0.0074	0.0015	18	89%
0.0082	0.0016	20	96%
0.0090	0.0018	22	97%
0.0098	0.0020	24	98%

Simulated power is based upon 10000 simulations of trials assuming 80% efficacy $\left(1 - \frac{\lambda_{AZD7442}}{\lambda_{Placebo}}\right)$, using Poisson regression model with robust variance, with no participants lost follow-up. Power is the proportion of trials with p-value < 0.05.

The sample size necessary to achieve the power for the primary endpoint is calculated based on the assumed attack rate in the placebo group and the 80% efficacy assumption, using Poisson regression model with robust variance.

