7.3. STATISTICAL TESTS

Statistical tests will be conducted at the two-sided 5% significance level. Confidence Intervals (CIs) will be two-sided with 95% coverage.

The null hypothesis for the primary endpoint is: efficacy of AZD7442 compared to placebo in preventing COVID-19 is equal to 0. Whereas, the alternative hypothesis is: efficacy of AZD7442 compared to placebo in preventing COVID-19 is not equal to 0. That is:

H0: efficacy = 0

HA: efficacy $\neq 0$

Primary efficacy will be presented with a 2-sided 95% CI, and statistical significance will be achieved if the lower bound of the 2-sided 95% CI is > 0. The success criterion for the study will be statistical significance.

If the statistical significance of the primary efficacy endpoint is demonstrated at two-sided alpha of 0.05, formal assessments of the key supportive estimands and key secondary estimand will be conducted at the primary analysis.

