16.1.3. PRIMARY ESTIMAND

The treatment condition of interest is single dose of AZD7442 (two IM injections, one for each mAb component, AZD8895 and AZD1061). The alternative treatment condition to which comparison will be made is a placebo.

The population of participants targeted in the primary estimand includes adults at least 18 years of age who have not had a prior SARS-CoV-2 RT-PCR-positive confirmed COVID-19 infection and who are candidates for benefit from passive immunization with antibodies, defined as having increased risk for inadequate response to active immunization (predicted poor responders to vaccines OR intolerant of vaccine), OR having increased risk for SARS-CoV-2 infection, defined as those whose locations or circumstances put them at appreciable risk of exposure to SARS-CoV-2 and COVID-19.

The primary endpoint (variable) to be obtained is a binary response, whereby a participant is defined as a COVID-19 case if their first case of SARS-CoV-2 RT-PCR-positive symptomatic illness occurs post dose of IMP prior to Day 183.

The primary estimand uses a while on treatment strategy. Data for participants who become unblinded to treatment assignment and/or take COVID-19 vaccine or other COVID-19 preventive product, in both cases prior to having met the criteria for the primary efficacy endpoint, are censored at the date of unblinding/receipt of first dose of COVID-19 preventive product, whichever is earlier.

The population-level summary measure is prophylactic efficacy, calculated as 1 – relative risk (RR). (RR is the incidence of infection in the AZD7442 group relative to the incidence of infection in the control group.)

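### The absolute risk reduction to Day 183 is a crude difference of proportions with no allowance for follow-up that ends early

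*SAP*

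**What the plan says.** SAP 16.1.6 presents the absolute risk reduction (ARR) in symptomatic RT-PCR-positive illness before Day 183, with a two-sided 95% Miettinen-Nurminen score interval. On computation it says: "The absolute risk reduction (ARR) will be implemented using the SAS PROC FREQ procedure".

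Other sections end follow-up before Day 183 for some participants:

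- **Data cut-off (SAP 4.4).** "The date for the DCO for this analysis will be the date that the 24th primary endpoint event is confirmed", or the date on which 30% of participants are unblinded if that comes first. Under SAP 16.1.4, participants still in the study have follow-up to the cut-off date only.
- **Intercurrent events (SAP 16.1.3).** Participants who are unblinded or take a preventive product before an event "are censored at the date of unblinding/receipt of first dose of COVID-19 preventive product, whichever is earlier".
- **Withdrawal (SAP 16.1.4).** Withdrawals are censored at last observation and counted as event-free. A participant with no post-baseline data contributes one day.

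The primary Poisson model in SAP 16.1.4 handles unequal follow-up with an offset for log time at risk. SAP 16.1.6 also plans a Cox model and Kaplan-Meier curves, but does not take the ARR from them. It does not say which intercurrent-event rule the ARR follows.

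**The concern.** In a 2x2 table every participant without an observed event counts as a full non-event, whether followed for one day or for 182. The result is the observed difference in proportions over whatever follow-up each arm had. It equals the Day-183 risk difference only if follow-up to that day is complete, or if arm differences in censoring happen to offset each other.

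Equal censoring largely cancels in a ratio but not in a difference: both proportions shrink, and so does the gap between them. The SAP therefore protects the relative measure and leaves the more exposed absolute measure uncorrected. A reader who takes the label at face value would carry the wrong absolute benefit forward, for example into a number needed to treat.

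**Working it through.** **1. The plan's own figures.** The SAP states no ARR, so I first checked that Table L is understood correctly. The inputs, all from SAP 7.1 and 7.3, are:

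- "Statistical tests will be conducted at the two-sided 5% significance level"
- "With at least 18 observed events, assuming 80% true efficacy, the study will have approximately 90% power"
- 2:1 allocation with arms of "the active group, n = approximately 3433) or saline placebo (the control group, n = approximately 1717) on Day 1"
- the last row of Table L, "0.0098 0.0020 24 98" (placebo rate, active rate, events, power in %)

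With total events n fixed, active-arm events are Binomial(n, π), where π = 3433·λ₁ / (3433·λ₁ + 1717·λ₀). The test is a Wald test on log RR, with variance (1 − p)/x summed over the arms (x = events, p = x/arm size). Exact enumeration gives 88.1%, 96.8%, 97.2% and 97.6% power at 18, 20, 22 and 24 events. The SAP states 89%, 96%, 97% and 98%. Table L reproduces to within 1 point.

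**2. What the 24-event row implies.** Expected events are 1717 × 0.0098 = 16.8 on placebo and 3433 × 0.0020 = 6.9 on active. The crude ARR is 0.98% − 0.20% = 0.78% (1/0.0078 = 128 treated per case avoided). With 17 and 7 events the Miettinen-Nurminen 95% interval is 0.37% to 1.39%.

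The same events can be rescaled to 182 days at constant hazard, with an **assumed** mean follow-up m in both arms: ARR = exp(−0.0020 × 182/m) − exp(−0.0098 × 182/m).

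| Assumed m (days) | Day-183 ARR |
|---|---|
| 182 | 0.78% |
| 150 | 0.94% |
| 120 | 1.17% |
| 90 | 1.56% |
| 60 | 2.32% |

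At 120 days the rescaled value still lies inside the crude interval. At 90 days it lies above it.

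**3. Ratio of crude to Day-183 ARR.** Assumptions: placebo risk 2% by Day 183, constant hazards, and efficacy 77% (the primary result in Protocol 2.3.2). Then h₀ = −ln(0.98)/182 = 0.000111 per day and h₁ = 0.23·h₀. The Day-183 ARR is 2.00% − 0.46% = 1.54%. An intercurrent-event risk q by Day 183 gives hazard g = −ln(1 − q)/182. The crude risk with potential follow-up c is h/(h + g) × [1 − exp(−(h + g)c)], averaged over c.

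| Potential follow-up (assumed) | q placebo / active | Crude ARR | Ratio |
|---|---|---|---|
| Uniform 30–120 days | 30% / 30% | 0.59% | 38% |
| Uniform 60–182 days | 30% / 30% | 0.90% | 59% |
| 182 days, no cut-off | 30% / 30% | 1.29% | 84% |
| 182 days, no cut-off | 40% / 25% | 1.16% | 76% |
| 182 days, no cut-off | 25% / 40% | 1.38% | 90% |
| 182 days, no cut-off | 10% / 50% | 1.56% | 102% |

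With no intercurrent events the first two ratios are 41% and 67%, so most of the shortfall there comes from the assumed follow-up range. The last four rows describe the final analysis, where the cut-off no longer shortens follow-up.

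**4. How much follow-up is lost.** The only related figure in the SAP is the 30% unblinding trigger. If exactly 30% were cut at mid-window, the retained fraction would be 0.70 + 0.30 × 0.5 = 0.85, a 15% understatement.

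A simulation applied the SAP's cut-off rule with assumed entry periods of 60 to 180 days, unblinding hazards of 0.0005 to 0.004 per day and two attack rates. The crude ARR was 0.36 to 0.87 of the Day-183 value. About 40% to 100% of participants were cut before Day 183.

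**The case against.** **The crude proportion may fit the estimand.** The endpoint is a binary response under a while-on-treatment strategy. The share of participants with an event before unblinding or vaccination can be read as the risk under that strategy. Kaplan-Meier censoring at those events instead estimates risk had they not occurred, if censoring is non-informative. That is closer to the hypothetical estimand specified separately in SAP 16.1.8.1. This stands for unblinding and vaccination, and it is a reason to state the rule. It does not cover data cut-off or withdrawal, which are plain losses of follow-up. The primary model already censors and time-adjusts for all of these.

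**Stronger readings are not supported.** A reader might infer that most follow-up is cut before Day 183. The documents give no enrolment period, median follow-up or share censored, and in some simulated scenarios fewer than half were cut. A reader might also infer that the ARR is always understated. The 10% / 50% row shows a slight reversal.

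**The consequences are limited.** The ARR is supplementary, outside the hierarchy in SAP 7.4 and not a success criterion. The SAP plans no number needed to treat, and Kaplan-Meier curves will sit beside the ARR. This stands, and it limits the weight of the point. But curves shown alongside do not correct a labelled estimate and its interval.

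**Conclusion.** The point holds in a conditional form. At an event-driven cut-off, the method in SAP 16.1.6 does not estimate the Day-183 risk difference that the section names. The crude ARR understates it when censoring is broadly similar in the arms or heavier on placebo.

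The size cannot be fixed from the documents. The illustrative ratios are 38% to 59% with staggered entry and an early cut-off, and about 84% at the final analysis with 30% intercurrent events in both arms. They rest on constant hazards, an assumed 2% placebo risk, 77% efficacy and assumed follow-up. The primary efficacy test is unaffected. What is at stake is the correctness of one reported absolute measure and its interval.

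**What to change.** In SAP 16.1.6, define the ARR as the difference between arms in Kaplan-Meier cumulative incidence at Day 183. If the risk set is too small at the cut-off, use the latest day at which it is adequate, by a criterion set in advance. Apply the primary analysis censoring, say that this is the intercurrent-event rule, and give a bootstrap or Greenwood 95% interval. If the PROC FREQ figure is kept, label it a crude observed difference and report follow-up time by arm beside it.

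The cost is SAP wording and little programming, because the Kaplan-Meier analysis is already planned. The interval will be somewhat wider. With about 24 events the estimate will lean on the late risk set, and a Greenwood interval may be weak where active-arm events are few. No change to design, data collection or hypothesis tests is needed.

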16.1.7. SUBGROUP ANALYSES FOR PRIMARY EFFICACY ENDPOINT

Subgroup analysis will be performed for the primary efficacy endpoint, SARS-CoV-2 RT-PCR-positive symptomatic illness occurring post dose of IMP and prior to Day 183. For subgroup analysis, FPAS will be used. Treatment-by-subgroup interaction will be tested using the Poisson regression with robust variance model adjusting for follow-up time with the terms of planned treatment, age group (Section 7.6), subgroup, and treatment-by-subgroup interaction, which will be implemented using PROC GENMOD procedure. If this full model does not achieve convergence, a reduced model of planned treatment, subgroup, and treatment-by-subgroup interaction will be considered. Within each level of a subgroup, the RRR and its corresponding 95% CI will be estimated using a Poisson regression model with robust variance with the term of treatment. A forest plot of the RRR and the 95% CI will be presented. If the CMH model is used for primary analysis (e.g. if the Poisson regression model fails to converge), a CMH model will also be used for subgroup analyses to generate the RRR and the corresponding 95% CI.

The subgroup analysis will be conducted for the subgroups in Section 7.7 on the FPAS population.

For subgroups corresponding to one of the factor levels included in the analysis model, the corresponding factor will not be included in the model. For example, the age group factor will not be included in the model for the analysis of participants ≤ 60 years old at the time of informed consent subgroup and analysis of participants ≥ 60 years old at

the time of informed consent subgroup.

No adjustment to the significance level for testing of all these subgroup analyses will be made since all these analyses will be considered supportive of the primary analysis.

16.1.8. ADDITIONAL ESTIMANDS FOR PRIMARY EFFICACY ENDPOINT

Additional estimands will also be used for the primary efficacy as shown in Table N:.

Table N: List of Additional Estimands for Primary Efficacy

		Attributes	S		
Label	Definition Population	Treatment Condition of Interest	Variable/ Endpoint	Intercurrent event handling strategy	Population-level summary measure
The efficacy	Full pre-exposure analysis set, defined as all	Single dose of	A binary	For participants who	Prophylactic
of a single	participants who were randomized, received at	AZD7442 (× 2 IM	response,	become unblinded to	efficacy, calculated
IM dose of	least one of the planned injections of IMP, and	injections, 1 for each	whereby a	treatment assignment	as 1-relative risk.
AZD7442	did not have a prior SARS-CoV-2 RT-PCR-	mAb component) or	participant is	and/or take COVID-19	(Relative risk is the
compared to	positive confirmed COVID-19 infection.	placebo	defined as a	vaccine or other COVID-	incidence of
placebo for	Targeted participants will have the following		COVID-19	19 preventive product, in	infection in the
the	characteristics:		case if their	both cases prior to having	AZD7442 group
prevention	Adults ≥ 18 years of age who are candidates for		first case of	met the criteria for the	relative to the
of COVID-	benefit from passive immunization with		SARS-CoV-	primary efficacy	incidence of
19 prior to	antibodies, defined as having increased risk for		2 RT-PCR-	endpoint, only data prior	infection in the
Day 183 –	inadequate response to active immunization		positive	to the intercurrent event	control group.)
Hypothetical	(predicted poor responders to vaccines OR		symptomatic	(i.e., up to the date of	
Estimand	intolerant of vaccine), OR having increased risk		illness	unblinding/receipt of first	
	for SARS-CoV-2 infection, defined as those		occurs post	dose of COVID-19	
	whose locations or circumstances put them at		dose of IMP	preventive product,	
	appreciable risk of exposure to SARS-CoV-2		and prior to	whichever is earlier) will	
	and COVID-19.		Day 183.	be considered and data	
				after the intercurrent	
				event will be imputed	
				(i.e., intercurrent events	
				will be handled using	
				hypothetical strategy).	

STATISTICAL ANALYSIS PLAN D8850C00002 – ed. V4.0

		Attributes	8		
Label	Definition Population	Treatment Condition of Interest	Variable/ Endpoint	Intercurrent event handling strategy	Population-level summary measure
				See Section 16.1.8.1.	
The efficacy	Full pre-exposure analysis set, defined as all	Single dose of	A binary	Participants who become	Prophylactic
of a single	participants who were randomized, received at	AZD7442 (× 2 IM	response,	unblinded to treatment	efficacy, calculated
IM dose of	least one of the planned injections of IMP, and	injections, 1 for each	whereby a	assignment and/or take	as 1-relative risk.
AZD7442	did not have a prior SARS-CoV-2 RT-PCR-	mAb component) or	participant is	COVID-19 vaccine or	(Relative risk is the
compared to	positive confirmed COVID-19 infection.	placebo	defined as a	other COVID-19	incidence of
placebo for	Targeted participants will have the following		COVID-19	preventive product, in	infection in the
the	characteristics:		case if their	both cases prior to having	AZD7442 group
prevention	Adults ≥ 18 years of age who are candidates for		first case of	met the criteria for the	relative to the
of COVID-	benefit from passive immunization with		SARS-CoV-	primary efficacy	incidence of
19 prior to	antibodies, defined as having increased risk for		2 RT-PCR-	endpoint, will be excluded	infection in the
Day 183 –	inadequate response to active immunization		positive	from analysis (i.e.,	control group.)
Principal	(predicted poor responders to vaccines OR		symptomatic	intercurrent events will be	
Stratum	intolerant of vaccine), OR having increased risk		illness	handled using principal	
Estimand	for SARS-CoV-2 infection, defined as those		occurs post	stratum strategy). The	
	whose locations or circumstances put them at		dose of IMP	principal stratum is the	
	appreciable risk of exposure to SARS-CoV-2		and prior to	stratum of participants	
	and COVID-19.		Day 183.	who did not experience an	
				intercurrent event	
				independent of	
				randomized treatment	
				assignment.	
The efficacy	A subset of the full pre-exposure analysis set,	Single dose of	A binary	Participants who become	Prophylactic

		Attributes	×.		
Label	Definition Population	Treatment Condition of Interest	Variable/ Endpoint	Intercurrent event handling strategy	Population-level summary measure
of a single IM dose of AZD7442 compared to placebo for the prevention of COVID- 19 prior to Day 183 – Per Protocol Estimand	defined as all participants who were randomized, received a full dose of IMP, who did not have a prior SARS-CoV-2 RT-PCR-positive confirmed COVID-19 infection, and who have no significant deviations from the protocol prior to Day 183 or meeting the primary endpoint (whichever occurs first). Targeted participants will have the following characteristics: Adults ≥ 18 years of age who are candidates for benefit from passive immunization with antibodies, defined as having increased risk for inadequate response to active immunization (predicted poor responders to vaccines OR intolerant of vaccine), OR having increased risk for SARS-CoV-2 infection, defined as those whose locations or circumstances put them at appreciable risk of exposure to SARS-CoV-2	AZD7442 (× 2 IM injections, 1 for each mAb component) or placebo	response, whereby a participant is defined as a COVID-19 case if their first case of SARS-CoV- 2 RT-PCR- positive symptomatic illness occurs post dose of IMP and prior to Day 183.	unblinded to treatment assignment and/or take COVID-19 vaccine or other COVID-19 preventive product, in both cases prior to having met the criteria for the primary efficacy endpoint, will be censored at the date of unblinding/receipt of first dose of COVID-19 preventive product, whichever is earlier (i.e., intercurrent events will be handled using a while on treatment strategy).	efficacy, calculated as 1-relative risk. (Relative risk is the incidence of infection in the AZD7442 group relative to the incidence of infection in the control group.)
	and Co 1D-17:				

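### The SAP's principal stratum row drops participants on an observed intercurrent event, so it estimates the stratum it names only under an unstated assumption that assignment does not affect those events; it should be relabelled.

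*SAP*

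**What the plan says.** SAP section 16.1.8, Table N, lists three additional estimands for the primary efficacy endpoint. In the Principal Stratum row, participants who become unblinded or take a COVID-19 vaccine or preventive product before meeting the primary "endpoint, will be excluded" from the analysis, and the row describes these events as "handled using principal" stratum strategy. The same cell defines the stratum as people who have no intercurrent event irrespective of the arm they were randomized to. The summary measure is one minus the relative risk.

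The Hypothetical row of the same table has its own section of steps (16.1.8.1). The Principal Stratum row has no estimator, identifying assumption, bounds or sensitivity analysis.

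Elsewhere in the SAP, the same participants are handled differently. The primary estimand censors them at the intercurrent event and keeps their earlier follow-up (16.1.3). The first key supportive estimand keeps them under treatment policy (16.1.9). The testing hierarchy (7.4) does not include the Principal Stratum row.

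The SAP covers the parent study. The supplied protocol is the repeat-dose sub-study addendum and has no such estimand.

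**The concern.** Membership of the defined stratum depends on two statuses: whether a person would have an intercurrent event on AZD7442, and whether the same person would have one on placebo. The exclusion rule uses only the status seen under the assigned arm. In general it therefore keeps stratum members plus some people who would have had an intercurrent event in the other arm, and that second part can differ between arms.

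A separate problem lies in the arithmetic. Exclusion applies only when the intercurrent event precedes the endpoint. A participant with COVID-19 first is kept as a case, while one who is case-free and then unblinded or vaccinated disappears together with the time at risk already served. Cases are kept and case-free time is lost.

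What is at stake is how a secondary figure is read. If the row agrees with the primary result, it may be taken as support from a causal estimand that it does not estimate. If it disagrees, the reason may be only that intercurrent events were more common in one arm.

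**Working it through.** **1. The plan's own figures.** SAP 7.1: "Approximately 5150 participants will be randomized in a 2:1 ratio" (3433 and 1717), with two-sided 5% tests (7.3). Table L assumes 80% efficacy, "with no participants lost follow-up", and does not model intercurrent events. Expected events in its last row are 1717 × 0.0098 + 3433 × 0.0020 = 16.8 + 6.9 = 23.7. With the event total fixed and split between arms at the Table L rates, a Wald test on the log relative risk has power 88.3, 96.9, 97.3 and 97.6% at 18, 20, 22 and 24 events, against the stated 89, 96, 97 and 98%. Table L reproduces, so its rates serve as the base case below. The Principal Stratum row states no figure to reproduce.

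**2. Does the retained group equal the stratum?** Let q1 and q0 be the shares with an intercurrent event on AZD7442 and placebo. The never-event stratum lies between max(0, 1 − q1 − q0) and min(1 − q1, 1 − q0).

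- At 30%/30% it is 40% to 70% of participants. In each arm 70% are retained, so 0.40/0.70 = 57% up to 100% of them belong to it.
- At 30%/50% it is 20% to 50%. Of the retained AZD7442 arm, 0.20/0.70 = 29% to 0.50/0.70 = 71% belong to it.

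Equal rates alone do not settle the matter. The upper limit at 30%/30% is reached only when the same people would have the event in either arm.

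**3. Effect on the rate in each arm.** Assume constant, independent hazards for COVID-19 and for intercurrent events over 182 days, full follow-up for everyone, and the primary model of 16.1.4, since the row names none. With a rare endpoint:

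- cases kept are proportional to q/(−ln(1 − q)), the mean fraction of follow-up before an intercurrent event, exactly as in the censoring analysis;
- person-time kept is proportional to 1 − q;
- the rate is multiplied by f(q) = q/[(1 − q)(−ln(1 − q))].

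For example, f(0.30) = 0.30/(0.70 × 0.357) = 1.20 and f(0.50) = 0.50/(0.50 × 0.693) = 1.44. At 30% in both arms, a placebo risk of 0.98% reads 0.98 × 1.20 = 1.18%. The follow-up offset cannot restore the time of people who are no longer in the data set.

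**4. Effect on the risk ratio.** The multiplier is f(q1)/f(q0). The shares are assumptions. The only related figure in the documents is the pooled 30% unblinding trigger (SAP 4.4).

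| Share, AZD7442/placebo | Pooled at 2:1 | f(q1) | f(q0) | Multiplier | RR read when the true RR is 0.203 |
|---|---|---|---|---|---|
| 30%/30% | 30% | 1.202 | 1.202 | 1.00 | 0.203 |
| 28%/34% | 30% | 1.184 | 1.240 | 0.955 | 0.194 |
| 25%/40% | 30% | 1.159 | 1.305 | 0.89 | 0.181 |
| 20%/50% | 30% | 1.120 | 1.443 | 0.78 | 0.158 |
| 50%/30% | 43% | 1.443 | 1.202 | 1.20 | 0.244 |

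The 0.203 is the ratio of the Table L rates for 24 events on the hazard scale. The censoring analysis gives 0.203 in every row.

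**5. Timing.** If intercurrent events are spread uniformly over follow-up, f(q) = (1 − q/2)/(1 − q). If they all fall uniformly in the first half, f(q) = (1 − 3q/4)/(1 − q).

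| Share, AZD7442/placebo | Uniform | First half only |
|---|---|---|
| 25%/40% | 0.875 | 0.93 |
| 20%/50% | 0.75 | 0.85 |

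**6. Scale against precision.** At 24 events split about 7 and 17, the standard error of log RR is √(1/7 + 1/17) = 0.45. The shifts are then |ln 0.955|/0.45 = 0.10, |ln 0.888|/0.45 = 0.26, |ln 0.777|/0.45 = 0.56 and ln 1.20/0.45 = 0.41 standard errors.

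**The case against.** The strongest reply is that the trial is double-blind and unblinding is itself an intercurrent event. Vaccination prompted by learning one's assignment comes after the first event and does not create it. The first request to unblind, or the first vaccination, is made while still blinded and may be balanced. If assignment does not affect intercurrent events, the retained participants are the stratum, apart from those whose COVID-19 case came first, and the row's phrase about independence from assignment could be read as expressing that premise. This is plausible, but the phrase defines a stratum and does not state an assumption, and no check of it is planned. Balanced rates are also a weaker condition than no effect of assignment on any individual.

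A second reply is that little depends on the row. It lies outside the hierarchy, and the same events are also handled by censoring, treatment policy and imputation. That stands and limits the weight of the point.

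A third is that the SAP already tabulates unblinding with reasons by planned group (9.1) and summarises concomitant medications by group (13). That would show much of any imbalance, but not the first intercurrent event before the endpoint, which is what the exclusion uses.

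A reader might infer that the exclusion biases the risk ratio in every case, or that it favours AZD7442. The documents support neither. The multiplier is 1.00 when shares are equal and efficacy does not vary with the propensity for intercurrent events. It exceeds 1 when AZD7442 has more of them, and no per-arm rates are given.

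**Conclusion.** The point holds as one of labelling and an unstated assumption, and it is minor. The rule in Table N does not in general estimate the stratum that the row defines. It does so only if assignment has no effect on intercurrent events, and even then participants whose case came first are kept without their status being known.

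Absolute rates are inflated in both arms. The risk ratio moves only if intercurrent events differ by arm, in frequency or in their relation to risk, or if efficacy varies with the propensity for them. Within the assumed range the multiplier runs from 0.78 to 1.20 under constant hazards, at most about 0.6 standard errors at 24 events. It changes with event timing, and the actual size and direction cannot be known from the documents.

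A reader might go further and infer that the efficacy conclusion is in doubt. It is not on this ground, because the success criterion (7.3) and the hierarchy (7.4) do not use this row.

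**What to change.** In Table N, rename the row as a descriptive analysis of participants without an observed intercurrent event. State that it is not to be interpreted as a principal-stratum causal effect or as robustness evidence for efficacy. Beside it, report by arm the number of participants whose first intercurrent event (unblinding, vaccine or other preventive product) preceded the endpoint.

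Principal-score weighting on baseline covariates would not cure the distortion shown above. That distortion arises even when intercurrent events are unrelated to covariates, in which case the weights would be constant within an arm. It comes from keeping case-first participants while deleting the time of those with intercurrent events.

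The cost is SAP wording and one small table. The primary analysis and testing hierarchy do not change. The only loss is one named estimand.
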